7.0 ADVERSE EVENTS

As per MDACC and Leukemia phase I-II studies (Appendix C and Appendix F). Toxicity will be scored using CTCAE Version 3.0 for toxicity and adverse event reporting. A copy of the CTCAE Version 3.0 can be downloaded from the CTEP homepage (<http://ctep.info.nih.gov>). All appropriate treatment areas should have access to a copy of the CTCAE Version 3.0. All adverse clinical experiences, whether observed by the investigator or reported by the patient, must be recorded, with details about the duration and intensity of each episode, the action taken with respect to the test drug, and the patient's outcome. The investigator

Commented [SM1]: Add appropriate appendix number

Commented [SM2]: Add appropriate appendix number here as well

must evaluate each adverse experience for its relationship to the test drug and for its seriousness.

Myelosuppression and associated complications are expected events during leukemia therapy and are part of the treatment success (marrow emptying of leukemic cells). Therefore, myelosuppression and associated complications such as fever, infections, bleeding and related hospitalizations will not be reported as individual ADRs, but will be summarized in the updated and final reports. Only prolonged myelosuppression, as defined by the new NCI criteria specific for leukemia, i.e., marrow cellularity < 5% on day 42 or later (6 weeks) from start of therapy without evidence of leukemia, will be reported as an ADR and considered in defining the maximum tolerated dose (MTD) and dose-limiting toxicity (DLT) of particular agents or regimens.

MD Anderson (Sponsor) Reporting Requirements for Serious Adverse Events and Dose Limiting Toxicities:

Serious Adverse Event (SAE) Definition

A serious adverse event is one that at any dose (including overdose):

- Results in death
- Is life-threatening¹
- Requires inpatient hospitalization or prolongation of existing hospitalization
- Results in persistent or significant disability or incapacity²
- Is a congenital anomaly or birth defect
- Is an important medical event³
- Suspected positive Pregnancy

¹“Life-threatening” means that the subject was at immediate risk of death at the time of the serious adverse event; it does not refer to a serious adverse event that hypothetically might have caused death if it were more severe.

²“Persistent or significant disability or incapacity” means that there is a substantial disruption of a person’s ability to carry out normal life functions.

³Medical and scientific judgment should be exercised in deciding whether expedited reporting is appropriate in situations where none of the outcomes listed above occurred. Important medical events that may not be immediately life-threatening or result in death or hospitalization but may jeopardize the patient or may require intervention to prevent one of the other outcomes listed in the definition above should also usually be considered serious. Examples of such events include allergic bronchospasm requiring intensive treatment in an emergency room or at home, blood dyscrasias or convulsions that do not result in inpatient hospitalization, or the development of drug dependency or drug

abuse. A new diagnosis of cancer during the course of a treatment should be considered as medically important.

Adverse Drug Reaction Reporting

Toxicity will be scored using CTCAE Version 3.0 for toxicity and adverse event reporting. A copy of the CTCAE Version 3.0 can be downloaded from the CTEP homepage (<http://ctep.info.nih.gov>). All appropriate treatment areas should have access to a copy of the CTCAE Version 3.0. All adverse clinical experiences, whether observed by the investigator or reported by the patient, must be recorded, with details about the duration and intensity of each episode, the action taken with respect to the test drug, and the patient's outcome. The investigator must evaluate each adverse experience for its relationship to the test drug and for its seriousness.

The investigator must appraise all abnormal laboratory results for their clinical significance. If any abnormal laboratory result is considered clinically significant, the investigator must provide details about the action taken with respect to the test drug and about the patient's outcome.

Serious Adverse Events Reporting: The principle investigator has the obligation to report all serious adverse events to the University of Texas M. D. Anderson Cancer Center (MDACC) IRB via the Office of Protocol Research and to Celgene within 24 hours.

In IND studies, all serious adverse events must be reported to the FDA by the investigator through the Office of Research Education & Regulatory Management (ORERM) as required by 21 CFR 312.32. These reports are to be filed utilizing the University of Texas M. D. Anderson Cancer Center Adverse Event Reporting Form. This includes serious, related, labeled (expected) and serious, related, unlabeled (unexpected) adverse experiences. All other serious adverse events not requiring expedited reporting should be reported to MDACC IRB and ORERM within 5 business days.

All deaths during treatment or within 30 days following completion of active protocol therapy must be reported within 24 hours of knowledge regardless of the attribution. SAEs beyond 4 weeks after the end of study drug administration will be reported if thought to be drug related.

NOTE: Instructions concerning procedures and reporting for pregnancies below.

Pregnancies

Pregnancies occurring while the subject is on lenalidomide or within 4 weeks after the subject's last dose of lenalidomide are considered expedited reportable events. If the subject is on lenalidomide, it is to be discontinued immediately and the subject is to be instructed to return any unused portion of lenalidomide to the Investigator. The pregnancy must be reported by the investigator to MDACC IRB and ORERM AND to

Celgene Corporation Worldwide Drug Safety Surveillance (WWDSS) within 24 hours of the Investigator's knowledge of the pregnancy by phone and facsimile using the SAE Form.

The Investigator will follow the subject until completion of the pregnancy, and must notify Celgene Corporation Worldwide Drug Safety Surveillance (WWDSS) of the outcome as specified below. The Investigator will provide this information as a follow-up to the initial SAE.

If the outcome of the pregnancy meets the criteria for immediate classification as a SAE (i.e., spontaneous abortion [any congenital anomaly detected in an aborted fetus is to be documented], stillbirth, neonatal death, or congenital anomaly), the Investigator should follow the procedures for reporting SAEs (i.e., report the event to Celgene Corporation Worldwide Drug Safety Surveillance (WWDSS) by facsimile within 24 hours of the Investigator's knowledge of the event) and report the event to MDACC IRB and ORERM.

Any suspected fetal exposure to lenalidomide must be reported to Celgene, MDACC IRB AND ORERM within 24 hours of being made aware of the event. The patient should be referred to an obstetrician/gynecologist experienced in reproductive toxicity for further evaluation and counseling.

All neonatal deaths that occur within 30 days of birth should be reported, without regard to causality, as SAEs. In addition, any infant death after 30 days that the Investigator suspects is related to the *in utero* exposure to lenalidomide should also be reported. In the case of a live "normal" birth, Celgene Corporation Worldwide Drug Safety Surveillance (WWDSS), MDACC IRB AND ORERM should be advised as soon as the information is available.

Celgene Drug Safety Contact Information:

Celgene Corporation
Worldwide Drug Safety Surveillance (WWDSS)
[name]
[name]

Toll Free: [contact]
[contact]
[contact]
e-mail: [contact]

Investigator Reporting Responsibilities

The conduct of the study will comply with all FDA safety reporting requirements. Serious Adverse Events Reporting: The principle investigator has the obligation to report all serious adverse events to the University of Texas M. D. Anderson Cancer

Center (MDACC) IRB via the Office of Protocol Research and also to Celgene within 24 hours.

IND Annual Reports

If the FDA has granted an IND number, it is a requirement of 21 CFR 312.33, that an annual report is provided to the FDA within 60-days of the IND anniversary date. 21 CFR 312.33 provides the data elements that are to be submitted in the report. The Annual Report should be filed with MD Anderson's ORERM, who will then forward to FDA. An additional copy should be placed in the study's Regulatory Binder and a copy must be sent to Celgene Corporation as a supporter of this study as follows.

Celgene Corporation
Attn: Medical Development
[name]
[name]
[contact]

All adverse experience reports must include the patient number, age, sex, weight, severity of reaction (mild, moderate, severe), relationship to study drug (probably related, unknown relationship, definitely not related), date and time of administration of test medications and all concomitant medications, and medical treatment provided. The investigator is responsible for evaluating all adverse events to determine whether criteria for "serious" and as defined above are present. The investigator is responsible for reporting adverse events to Celgene as described below.

Expedited reporting by Principal Investigator to Celgene

Serious adverse events (SAE) are defined above. The investigator should inform Celgene of any SAE within 24 hours of being aware of the event. The date of awareness should be noted on the report. This must be documented on an MD Anderson SAE form. This form must be completed and supplied to MDACC IRB, ORERM and Celgene within 24 hours/1 business day at the latest on the following working day. The initial report must be as complete as possible, including details of the current illness and (serious) adverse event, and an assessment of the causal relationship between the event and the investigational product(s). Information not available at the time of the initial report (e.g., an end date for the adverse event or laboratory values received after the report) must be documented on a follow-up MD Anderson SAE form. A final report to document resolution of the SAE is required. The Celgene protocol number (RV-MF-PI-0102) should be included on SAE reports to Celgene. A copy of the fax transmission confirmation of the SAE report to Celgene should be attached to the SAE and retained with the patient records.

Report of Adverse Events to the Institutional Review Board

The principal Investigator is required to notify his/her Institutional Review Board (IRB) of a serious adverse event according to institutional policy.

Sponsor Reporting to the FDA

Adverse drug reactions that are **Serious, Unlisted/unexpected, and at least possibly associated to the drug**, and that have not previously been reported in the Investigators brochure, or reference safety information document should be reported promptly to the Food and Drug Administration (FDA) in writing by each investigator/physician engaged in clinical research. A clear description of the suspected reaction should be provided along with an assessment as to whether the event is drug or disease related.

The sponsor shall notify the FDA by telephone or by fax of any unexpected fatal or life threatening experience associated with the use of the drug. As soon as possible, but no later than 7 calendar days after the sponsors initial receipt of the information. Each phone call or fax shall be transmitted to the FDA new drug review division in the Center for Drug Evaluation and Research or the product review division in the Center for Biologics Evaluation and Research that has responsibility for review of the IND if applicable.

Adverse event updates/IND safety reports

Celgene shall notify the Investigator via an IND Safety Report of the following information:

- Any AE associated with the use of study drug in this study or in other studies that is both serious and unexpected.
- Any finding from tests in laboratory animals that suggests a significant risk for human subjects including reports of mutagenicity, teratogenicity, or carcinogenicity.

The Investigator shall notify his/her IRB/EC promptly of these new serious and unexpected AE(s) or significant risks to subjects.

The Investigator must keep copies of all AE information, including correspondence with Celgene and the IRB/EC, on file.

Protocol amendments

Any amendment to this protocol must be agreed to by the Principal Investigator and reviewed by Celgene. Amendments should only be submitted to IRB/EC after consideration of Celgene review. Written verification of IRB/EC approval will be obtained before any amendment is implemented.

Protocol deviations

When an emergency occurs that requires a deviation from the protocol for a subject, a deviation will be made only for that subject. A decision will be made as soon as possible to determine whether or not the subject (for whom the deviation from protocol was effected) is to continue in the study. The subject's medical records will completely describe the deviation from the protocol and state the reasons for such deviation. In addition, the Investigator will notify the IRB/EC in writing of such deviation from protocol.

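### In the text available, section 7.0 gives two reporting instructions for a serious myelosuppression-related event (summary only, or individual report within 24 hours) and does not say which governs

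*Combined protocol and SAP*

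**What the plan says.** All of this is in section 7.0 of the combined protocol and SAP.

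- **The summary-only clause.** Before the SAE definitions, the section calls myelosuppression and its complications "expected events during leukemia therapy and are part of the treatment success (marrow emptying of leukemic cells". It concludes that "fever, infections, bleeding and related hospitalizations will not be reported as individual ADRs, but will be summarized in the updated and final reports". The exception is narrow: "Only prolonged myelosuppression, as defined by the new NCI criteria specific for leukemia", meaning marrow cellularity below 5% at day 42 or later without leukemia, is reported as an ADR and counts toward the MTD and DLT.
- **The SAE definition.** A new heading on the sponsor's requirements for SAEs and dose-limiting toxicities follows. One of its criteria is "Requires inpatient hospitalization or prolongation of existing hospitalization", with no exclusion for myelosuppression.
- **The SAE reporting duty.** Under the heading "Adverse Drug Reaction Reporting", the text reads "The principle investigator has the obligation to report all serious adverse events" to the IRB and the drug supplier within 24 hours. The duty is restated under Investigator Reporting Responsibilities. The subsection on expedited reporting to the supplier repeats it for any SAE.
- **Documents referred to.** The section opens "As per MDACC and Leukemia phase I-II studies (Appendix C and Appendix F", and a later subsection leaves IRB notification of SAEs to institutional policy. Neither the two appendices nor the policy was in the text available for this review.

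**The concern.** A patient admitted with an infection during neutropenia falls under both rules. One says summarize; the other says report individually within 24 hours. Staff who follow the first would be complying with a written sentence of the protocol.

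The stake is oversight while the trial runs. Safety is the secondary objective (section 1.2), and the only numerical stopping rule in section 9.0 is based on response. Individual SAE reports are therefore an important way for the IRB and the supplier to see toxicity across patients during accrual, and section 8.0 lets the supplier end the study for medical reasons. Under the clause, non-fatal serious cytopenia-related events would reach them only in periodic and final reports.

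**Working it through.** The point is textual, so no formula applies. The check follows one event through each rule in 7.0 and then looks for a sentence that ranks the rules.

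**Test event:** a non-fatal inpatient admission for infection during drug-related neutropenia, with marrow cellularity not below 5% at day 42.

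| Rule in 7.0 | Does it cover the event? | Instruction | Timing |
|---|---|---|---|
| Summary-only clause | Yes; infections and related hospitalizations are named | No individual ADR report | Updated and final reports; no interval stated |
| Exception for prolonged myelosuppression | No; its marrow criterion is not met | None | None |
| SAE definition, hospitalization criterion | Yes | Classed as an SAE | None |
| IRB and supplier duty, stated twice | Yes; all SAEs | Report | 24 hours |
| Supplier duty under expedited reporting | Yes; any SAE | Report | 24 hours |
| Route for SAEs not needing expedited reporting | Only if the event is judged not to need it | Report to the IRB and the institution's regulatory office | 5 business days |

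The same event is thus summary only under one rule and reportable under the others.

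**Search for a ranking sentence.** The reporting sentences of 7.0 contain no exception, override or cross-reference linking the clause to the SAE rules. The two nearest candidates do not settle it. The 5-business-day sentence sets a slower route but still requires a report, and it does not mention the clause. The institutional-policy sentence concerns the IRB only and leaves the separate duty to the supplier untouched.

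**Extent of the overlap.** The footnote on important medical events gives blood dyscrasias without admission as an example of what is usually considered serious. The overlap is therefore not limited to hospitalizations.

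**Fit of the rationale.** The clause treats myelosuppression as evidence of success in leukemia. In section 6.0, complete response requires pretreatment cytopenias to resolve, and partial response and hematologic improvement credit rises in neutrophils, hemoglobin and platelets. Section 5.2 lists severe neutropenia and thrombocytopenia as adverse events that interrupt lenalidomide. The premise of the clause does not carry over to this trial.

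**Size.** The documents give no hospitalization rate on lenalidomide in myelofibrosis, so no count of affected SAEs can be derived.

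**The case against.** The strongest reply is that the rules can be reconciled. The clause speaks of individual ADRs. A new heading then opens a separate SAE regime in which the duty is stated without exception each time. On that reading the clause covers only events that are not serious, and the SAE rules prevail. This is plausible and may be what was intended.

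It is not what the text says. The clause names hospitalizations, and under the SAE definition an inpatient hospitalization is serious, so the non-serious reading leaves that word almost no content. Two further textual points carry little weight. The 24-hour sentence stands under an ADR heading, but it has its own SAE label and recurs elsewhere under a different heading. The FDA subsection speaks of serious adverse drug reactions, but it adds the qualifier, so it does not equate the terms.

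A second reply is that the leukemia wording looks like carried-over text that staff may not apply. That may be so, and in that case the amendment adds no reports. It is no reason to leave the sentence in force unqualified.

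A third reply is that Appendices C and F or the institutional policy may already set the order. This stands as a limit: the finding covers the available text of 7.0, not the whole protocol.

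There are also backstops. Section 8.0 gives the institution's regulatory office and the supplier direct access to source documents at monitoring and audit. That narrows the consequence but does not replace a 24-hour report.

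**Conclusion.** The conflict is real and should be fixed. It is a matter of safety reporting, not of the analysis: no estimate or decision rule in section 9.0 changes. If the clause is followed, the effect is limited to individual and expedited reporting of non-fatal serious cytopenia-related events. The difference in timing is 24 hours (or 5 business days on the slower route) against no stated interval.

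Four stronger readings are tempting, and the documents do not support them.

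- *Events are lost from the safety data.* Section 7.0 still requires all adverse experiences to be recorded, section 5.8 continues the blood counts, and section 9.0 lists and tabulates adverse events. Deaths on treatment or within 30 days of completing it are reported within 24 hours whatever the cause.
- *The trial under-reports SAEs.* The documents do not show which rule is followed in practice.
- *The duty to report expected events to the FDA is breached.* That passage begins "In IND studies, all serious adverse events must be reported to the FDA", and the annual-report paragraph leaves open whether an IND was granted. The finding does not rest on it.
- *The effect can be sized from the single-agent myelofibrosis study in section 2.2.* That study reports severe cytopenias, not admissions.

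The conclusion assumes that nothing in Appendices C and F or the institutional policy already ranks the two rules.

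**What to change.** Reconcile the passages with one sentence in 7.0, placed directly after the clause: the summary-only provision does not apply to any event meeting the SAE definition, including fever, infection, bleeding or hospitalization related to myelosuppression, and such events are reported individually under the SAE rules of this section.

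Keep the sentence on prolonged myelosuppression. It defines an ADR and feeds the DLT definition, and removing the whole clause could take it out as well. Before submitting the amendment, check the wording against Appendices C and F and the institutional policy cited under IRB reporting.

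The cost is a one-sentence amendment. There may be some additional SAE reports if the clause is now being followed, and none if the SAE rules already prevail in practice. No dose or clinical rule changes.

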In 2 phase I studies in multiple myeloma, a total of 41 patients have been treated with lenalidomide. In one study at the University of Arkansas, 15 patients who relapsed or were refractory to high dose melphalan therapy with stem cell transplant were treated for 4 weeks in an open-label safety study and were permitted to continue therapy in an extension phase of the trial. Patient cohorts were treated at the following daily doses: 5mg, 10mg, 25mg, and 50mg. In a similar study at the Dana Farber Cancer Institute, 27 patients with rapidly advancing refractory multiple myeloma were enrolled. Anti-myeloma activity was observed in each of these 2 phase I studies. Decreases in neutrophil and platelet counts were the dose-limiting toxicities associated with lenalidomide. The maximum tolerated dose (MTD) was not reached within 28 days. Due to dose modifications associated with myelosuppression observed beyond Day 28 at the 25mg and 50mg daily dose levels, the dose schedule most widely used in future studies has been lenalidomide on Days 1-21, repeated every 28 days.

Pharmacokinetic analyses were performed on 15 multiple myeloma patients treated in the phase I studies. Absorption was found to be rapid on both Day 1 and Day 28 with time to maximum blood levels ranging from 0.7 to 2.0 hours at all dose levels (5mg, 10mg, 25mg, and 50mg). Plasma lenalidomide declined in a monophasic manner with elimination half-life ranging from 2.8 to 6.1 hours on both Day 1 and 28 at all 4 doses. No plasma accumulation was observed with multiple daily dosing. Peak and overall plasma concentrations were dose proportional over the dosing range of 5mg to 50mg.

A multicenter, randomized, phase II trial compared 2 syncopated dose schedules of lenalidomide used alone or in combination with dexamethasone in the treatment of relapsed or refractory multiple myeloma. All patients were treated on Days 1-21 of a 28-day cycle. Patients treated with 15mg BID experienced more myelosuppression and dose reductions compared with patients treated with 30mg daily. Anti-myeloma activity was observed with each dose and schedule of single agent lenalidomide. The addition of dexamethasone to lenalidomide yielded responses in some patients who had not responded to lenalidomide alone.

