5.0 TREATMENT PLAN

The planned dose and schedule of investigation of lenalidomide is 10 mg/day orally (unless blood platelet count is below $100 \times 10^9/L$, in which case the starting dose of lenalidomide is 5 mg/day). Lenalidomide will be taken orally in the morning each day on days 1-21, followed by 7 days of no therapy of each 28-day cycle.

Lenalidomide capsules should be swallowed whole, and should not be broken, chewed or opened. If a dose of lenalidomide is missed, it should be taken as soon as possible on the same day. If it is missed for the entire day, it should not be made up.

Patients who take more than the prescribed dose of lenalidomide should be instructed to seek emergency medical care if needed and contact study staff immediately. Twenty eight days is considered one cycle of therapy. Attempts will be made to provide an adequate treatment period of at least 6 months unless significant toxicity observed, to account for delayed time to response observed with biologic agents. Responders will continue therapy for 2 years unless progression of disease or toxicity warranting discontinuation of therapy is observed.

Prednisone will be used orally at the dose of 30 mg/day during cycle 1, 15 mg/day during cycle 2, and 15 mg every other day during cycle 3, and then it will be discontinued.

All patients will be registered on the Patient Data Management System (PDMS) at MD Anderson Cancer Center after the informed consent is signed. Medication will be mailed to participants, per the RevAssist® Program.

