5.4 Initiation of a New Cycle of Therapy

A new course of treatment may begin on the scheduled Day 1 of a new cycle if:

- The ANC is $\geq 1,000/\mu\text{L}$;
- The platelet count is $\geq 50 \times 10^9/\text{L}$ if $\geq 100 \times 10^9/\text{L}$ before starting therapy, or at least 50% of the pre-therapy value if $< 100 \times 10^9/\text{L}$ before starting therapy;
- Any lenalidomide-related allergic reaction/hypersensitivity or sinus bradycardia/ other cardiac arrhythmia adverse event that may have occurred has resolved to \leq grade 1 severity;
- Any other lenalidomide-related adverse event that may have occurred has resolved to \leq grade 2 severity.

If these conditions are not met on Day 1 of a new cycle, the subject will be evaluated weekly and a new cycle of lenalidomide (with/without prednisone after cycle 3) will not be initiated until the toxicity has resolved as described above.

If lenalidomide dosing was omitted for the remainder of the previous cycle or if the new cycle is delayed due to toxicity newly encountered on the scheduled Day 1, then the new cycle will be started with a one-level dose reduction. If the toxicity has not resolved as described above within 4 weeks, the patient will discontinue treatment. In unusual circumstance this rule may be modified by Principal Investigator if felt to be in the best interest of the patient (for example, responding patient with neutropenia or low platelets, that resolve past 4 weeks may be restarted on therapy); this case must be fully documented.

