5.8 Evaluation During Study

Time parameters for mandatory evaluations during the study are: +/-5 days for blood tests, +/- two weeks for bone marrow exams, and +/-2 weeks for MD Anderson visits. Exception for these rules can be made in unusual circumstances (e.g. long holiday) if approved by Principal Investigator and documented.

- Follow up visits at MD Anderson are required initially monthly (+/- 1 week), with review of constitutional symptoms and physical exam. Following the completion of cycle 3, patients that are on a stable dose of lenalidomide and have no serious drug related side effects, and the physician feels it is in the patients best interest, may return to MDA every three months. Following the completion of cycle 24, patients that are on a stable dose of lenalidomide, have no serious drug related side effects, and the physician feels it is in the patients best interest, may return to MDA every 6 months (+/-2 weeks). Only one, 28 day supply of Lenalidomide may be provided to a patient per monthly cycle. In this case, a monthly phone assessment of toxicity, review of required blood tests (pregnancy test if applicable) and confirmation of the requirements for the initiation of a new cycle must be done.
- CBC with differential every other week x 8, then every 1 month or more frequently as clinically indicated. Following the completion of cycle 24, CBC every 1-3 months while participating on the study.
- Bone marrow aspiration and biopsy every 3 months (to include staining for fibrosis); cytogenetics every 3 months if abnormal prior to therapy; JAK2 mutation analysis every 3 months if mutation present prior to therapy. Following the completion of Cycle 24, bone marrow aspiration and biopsy every year, cytogenetics every year if abnormal prior to therapy; JAK2 every year if mutation present prior to therapy.
- Serum BUN, alkaline phosphatase, creatinine, bilirubin, ALT, sodium, potassium, chloride, carbon dioxide, glucose, lactate dehydrogenase every other week x 6, then every 1 month. Following the completion of cycle 24, complete every 3-6 months while participating on the study
- TSH every 3 months. Following the completion of Cycle 24, TSH every 6 months.
- CD34+ cell counts in blood every 3 months. Following the completion of Cycle 24 CD34+ every year.
- Serum or urine pregnancy test (sensitivity of at least 50 mIU/mL) every week x 4, then monthly for all FCBP with regular menstrual cycles, or every 2 weeks if irregular cycles.

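### Section 7.0 reports myelosuppression individually only on a leukemia marrow-cellularity criterion, while this myelofibrosis protocol judges marrow toxicity by ANC and platelets

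*Combined protocol and SAP*

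**What the plan says.** Section 7.0 treats myelosuppression and its complications as expected, on the reasoning that emptying the marrow of leukemic cells is part of success. These events "will not be reported as individual ADRs, but will be summarized in the updated and final reports". The exception is narrow: "Only prolonged myelosuppression, as defined by the new NCI criteria specific for leukemia", which the section spells out as "marrow cellularity < 5% on day 42 or later (6 weeks) from start of therapy without evidence of leukemia". No ANC or platelet equivalent is offered.

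Elsewhere the protocol works from blood counts:

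- Section 5.2 triggers its hematologic actions on ANC and platelets.
- Section 5.4 sets ANC and platelet limits for starting a new cycle, requires weekly evaluation during a delay, and states: "If the toxicity has not resolved as described above within 4 weeks, the patient will discontinue treatment". The Principal Investigator may modify this in unusual circumstances.
- Section 6.0 counts rises in ANC, hemoglobin and platelets toward response.
- Section 2.2, on the phase I myeloma studies, says: "Decreases in neutrophil and platelet counts were the dose-limiting toxicities associated with lenalidomide".

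Marrow is examined on a calendar. Section 5.8 schedules "Bone marrow aspiration and biopsy every 3 months (to include staining for fibrosis"), with a tolerance of plus or minus "two weeks for bone marrow exams". The supplied text calls for no marrow at day 42 and none when counts fail to recover.

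**The concern.** The reporting threshold was written for a different disease. In leukemia a hypocellular marrow can be the aim of treatment, so only its undue persistence is reported. In this trial falling counts are not the aim; Section 6.0 scores the reverse as benefit. The protocol's own sign of serious marrow toxicity is counts that stay below the Section 5.4 limits long enough to end treatment. Followed as written, Section 7.0 does not make that event an individual ADR unless a marrow happens to be done and happens to be below 5% cellular.

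What is at stake is oversight while the trial runs. Section 2.3 says lenalidomide with steroids has not been tried in MF, and safety is the secondary objective (Section 1.2). Section 9.0 has an early stopping rule for response and none for toxicity, so individual reports are a main way for serious marrow toxicity to come to attention before the summary reports.

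**Working it through.** There is no design figure to reproduce. The check has two parts: whether the criterion fits the event, and whether the schedule supplies the measurement.

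**1. Fit of the criterion**

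| | ADR criterion (7.0) | Toxicity rules (5.2, 5.4) |
|---|---|---|
| Measured on | marrow cellularity | ANC and platelets |
| Threshold | below 5% | count limits, platelets relative to baseline if it was low |
| When assessed | at a marrow, day 42 onward | CBCs, and weekly during a delay |

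The two can disagree. Section 2.1 describes extensive fibrosis in advanced MF, so counts may stay low with a marrow that is fibrotic or cellular and not below 5%. Such a patient fails the ADR criterion whenever the marrow is taken. This part does not depend on timing.

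**2. Timeline**

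Inputs:

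- Cycle length: "Twenty eight days is considered one cycle of therapy" (Section 5.0).
- Four-week limit (Section 5.4), counted here from the scheduled Day 1 of the next cycle.
- First on-study marrow at 3 months, within 14 days either side (Section 5.8), counted here from the start of therapy.

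Formulas, with the first dose on day 1 and onset in cycle c:

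- Next scheduled Day 1 = 1 + 28c
- Four-week limit = 1 + 28c + 28
- First marrow = 1 + 84 = day 85 (three 28-day cycles) or 1 + 91 = day 92 (three calendar months)
- Window = day 71 to 99, or day 78 to 106

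| Onset cycle | Next scheduled Day 1 | Four-week limit | Against the first marrow |
|---|---|---|---|
| 1 | 29 | 57 | 71 − 57 = 14 to 78 − 57 = 21 days before the window opens |
| 2 | 57 | 85 | inside the window on either count |
| 3 | 85 | 113 | 113 − 92 = 21 to 113 − 85 = 28 days after the nominal marrow |

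For cycle 1, day 57 is already past day 42. The time condition of the ADR criterion is met, but no scheduled marrow exists to test cellularity.

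**3. How many patients**

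The documents give no rate of count non-recovery. The closest data are in the single-agent MF study in Section 2.2: grade 3 or higher thrombocytopenia in 2 patients and neutropenia in 1. If these were different patients, that is 3/41 = 7% of those treated, or 3/20 = 15% if the evaluable patients are the denominator; the text does not say which. Scaled to 41 patients, that is 3 to about 6 (0.15 × 41 = 6.2) with any such event. Those who do not recover would be a subset.

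**The case against.** The strongest reply is that little is lost:

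- Section 7.0 requires every adverse experience to be recorded with duration, intensity, action and outcome, and to be assessed for relatedness and seriousness.
- Section 5.10 records the date of and reason for discontinuation.
- Section 9.0 lists and tabulates adverse events.
- Serious events go to the IRB and the drug supplier within 24 hours, and Section 7.0 names blood dyscrasias as a possible important medical event.
- No decision in Section 9.0 uses the marrow threshold.

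All of this stands. It shows that the data survive, not that these events are reported individually. Without hospitalization the SAE route rests on judgment, and Section 7.0's restriction to prolonged, marrow-defined suppression gives an investigator a reason in the text not to report. The section also excludes related hospitalizations from individual ADR reports while its SAE definition includes hospitalization; those statements need reconciling too.

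A reader might infer that early marrow toxicity cannot meet the criterion. The documents do not support that. The criterion has no upper time limit, nothing bars an unscheduled marrow, Section 5.10 requires an attempt at final-visit evaluations, and the four-week rule can be modified. Section 5.8 also asks for a biopsy, so a dry tap need not prevent a cellularity reading.

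A reader might also take the MDS rates in Section 2.2 (35% to 58% with dose delays or reductions) to mean 14 to 24 of 41 patients. Those rates count dose changes in another disease, partly on other schedules and doses, and not non-recovery.

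Finally, Section 6.0 warns that drug-induced and disease-related myelosuppression are hard to separate. A count trigger will therefore catch some disease-driven cytopenia, and this part of the objection also stands.

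**Conclusion.** The concern holds in a limited form. The only ADR criterion for myelosuppression is borrowed from leukemia and does not match the way this MF protocol defines marrow toxicity. Persistent cytopenia with a marrow at or above 5% cellularity never meets it. For counts unrecovered after cycle 1, no scheduled marrow in the supplied text falls before the day 57 limit; the shortfall is 14 to 21 days. That timing gap is certain by schedule for cycle 1 only.

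The number of patients affected is unknown and may be small. Neither the efficacy analysis nor the planned adverse event tabulation is distorted; the weakness is in individual reporting during the trial.

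The timeline assumes that cycles start on schedule and that the four weeks run from the scheduled Day 1. Counting from onset within cycle 1 would bring the limit earlier (onset on day 15 gives day 43) and widen the gap. Section 7.0 defers to Appendices C and F, and Section 5.8 to Appendix K. None is in the supplied text, and any of them could add count-based reporting or an end-of-treatment marrow.

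**What to change.** In Section 7.0, remove the leukemia rationale. Keep the marrow criterion and add beside it a count-based ADR trigger: ANC or platelets still below the existing Section 5.4 limits four weeks after the scheduled Day 1 of the new cycle, whether or not treatment is then stopped. Apply the investigator's relatedness assessment that Section 7.0 already requires, so that disease-driven cases can be identified as such.

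In Section 9.0, give these events their own line in the adverse event tables. Reconcile Section 7.0 with Sections 5.4 and 5.8, and with its own SAE reporting requirement, so that the reportable event is one the scheduled assessments can detect.

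No dosing, stopping or visit rule changes, and the weekly evaluations needed are already required during a delay. The cost is one amended definition and a few more reports, some of them for cytopenia due to the disease.
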